9.4 Randomisation procedures

A bespoke web-based system with 24-hour availability will be developed for randomisation. Randomisation will use a 1:1 allocation ratio between arms and be stratified by site. Random permuted blocks of sizes 4 and 6 will be used within strata.

Patients will be randomised by a delegated member of the research team. The database is accessible via the NHS computers on site, with access only given to delegated members of the research team. Following randomisation, confirmation e-mail will be sent to the member of the research team randomising. This will be included in the patient's medical records and in the ISF.

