Given (i) 80% statistical power, (ii) a 10% alpha level, (iii) a trial sample size of 282 participants, (vi) a 75% 30-day survival probability in the control arm, (v) no survival difference between trial arms, and (vi) the proportional hazards assumption, the non-inferiority margin identified comprises a hazard ratio of 1.83 (HR=1.83). This equates to a 30-day survival probability non-inferiority margin of 0.59. A 10% alpha level is selected given that, for mortality, committing a Type I error is considered less concerning and identifying a difference between intervention and control arms if a difference truly exists is prioritised.

Table 1: Non-inferiority margins* identified for survival & binary outcomes

Outcome metric \geq	Statistical power	
	80%	90%
Survival outcome		
Hazard ratio (HR)	1.83	2.05
30-day survival probability	0.59	0.55
Binary outcome		
Absolute risk difference (ARD)	0.11	0.13

*Assuming a 10% alpha level, a trial sample size of 282 participants, a 75% 30-day survival probability,

no difference in survival between trial arms, and proportional hazards

A causal mediation analysis will be conducted to assess whether the effect of receiving the intervention treatment on the primary outcome is mediated through metabolite panels traits considered as Principal Components.⁷⁹ The traits included in the panel will be determined in the mechanistic outcomes analysis. Participant baseline characteristics will be summarised using suitable descriptive statistics for central tendency and variability.

An unmatched win ratio approach will be used as a secondary analysis to assess net clinical benefit. The win ratio treatment effect will be estimated using hierarchically (in this order) the outcomes 30-day mortality (yes/no), 30STS, and Barthel Index 30 days after randomisation. More emphasis will be placed on the win ratio analysis if relevant differences in mortality are observed. A full statistical analysis plan will be prospectively developed.

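### Table 1 puts one 10% alpha of unstated sidedness on both mortality margins, but the hazard-ratio row fits one-sided 5% and the risk-difference row one-sided 10%

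*Protocol*

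**What the plan says.** Section 12.1 of the protocol rests the survivor analysis of the primary outcome on the assumption that neither feed affects mortality, and says that mortality will be tested formally for non-inferiority at the end of the trial. The inputs begin: "Given (i) 80% statistical power, (ii) a 10% alpha level, (iii) a trial sample size of 282 participants". They go on to "a 75% 30-day survival probability in the control arm", equal survival in the two arms and proportional hazards. The text then names its margin: "the non-inferiority margin identified comprises a hazard ratio of 1.83 (HR=1.83", and converts it to a 30-day survival of 0.59. The 10% level is justified on the ground that a Type I error matters less for mortality than missing a true difference. Nothing says whether it is one- or two-sided.

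Table 1 is titled as giving margins for survival and binary outcomes. At 80% and 90% power it prints:

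- hazard ratio 1.83 and 2.05;
- 30-day survival 0.59 and 0.55;
- absolute risk difference 0.11 and 0.13.

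Its single footnote covers every row: "Assuming a 10% alpha level, a trial sample size of 282 participants, a 75% 30-day survival probability", then "no difference in survival between trial arms, and proportional hazards".

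**The concern.** All rows of Table 1 share the same alpha, sample size, control survival and null difference, so one reading of the alpha should return all of them. If it does not, at least one printed margin does not have the power shown above it, and the error rate of the mortality test is left open.

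That matters because this test supports the assumption behind the survivor analysis. Even with the margin held at HR 1.83, sidedness can decide the result. With about 70.5 deaths the standard error of the log hazard ratio is about 2/√70.5 = 0.238. The largest observed hazard ratio that would still show non-inferiority is 1.83 × exp(−1.645 × 0.238) = 1.24 at one-sided 5%, and 1.83 × exp(−1.282 × 0.238) = 1.35 at one-sided 10%. An observed hazard ratio of 1.30 would fail under one reading and pass under the other.

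**Working it through.** **Inputs**

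- Total 282 (section 12.1). Section 9.4 gives the allocation: "Randomisation will use a 1:1 allocation ratio between arms and be stratified by site". Hence 141 per arm.
- Control survival 0.75, so mortality 0.25, and no true difference (section 12.1). Expected deaths d = 282 × 0.25 = 70.5; √d = 8.396.
- Power 80% and 90% (Table 1): z = 0.842 and 1.282.
- Alpha 10%, sidedness not given. One-sided 10% has z = 1.282. Two-sided 10% is one-sided 5%, z = 1.645.
- Sums of z: one-sided 10%, 2.123 (80%) and 2.563 (90%); one-sided 5%, 2.486 and 2.926.

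**Survival row.** Under proportional hazards, 0.75^1.83 = 0.591 and 0.75^2.05 = 0.554. These give the printed 0.59 and 0.55, so this row only restates the hazard-ratio row.

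**Risk-difference row.** Margin = (z_alpha + z_power) × √(2 × 0.25 × 0.75/141) = (z_alpha + z_power) × 0.0516.

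**Hazard-ratio row.** Schoenfeld: HR = exp(2(z_alpha + z_power)/√d). Freedman: HR = (k + 1)/(k − 1), with k = √d/(z_alpha + z_power).

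| | Printed, 80% / 90% | One-sided 10% | One-sided 5% |
|---|---|---|---|
| Risk difference | 0.11 / 0.13 | 0.1095 / 0.1322 | 0.1282 / 0.1509 |
| HR, Schoenfeld | 1.83 / 2.05 | 1.658 / 1.841 | 1.808 / 2.008 |
| HR, Freedman | 1.83 / 2.05 | 1.677 / 1.879 | 1.841 / 2.070 |

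The risk-difference row rounds to the printed values at one-sided 10% and misses them at one-sided 5%. The printed hazard ratios lie between the two formulas at one-sided 5% in both columns, and well above both at one-sided 10%.

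**Power of the printed margins**

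- HR 1.83: Schoenfeld power is Φ(√d × ln 1.83/2 − z_alpha), Freedman power is Φ(√d × 0.83/2.83 − z_alpha). One-sided 5%: 81.4% and 79.3%. One-sided 10%: 89.5% and 88.1%.
- HR 2.05: one-sided 5%, 91.5% and 89.4%; one-sided 10%, 95.8% and 94.6%.
- Risk difference 0.11: Φ(0.11/0.0516 − z_alpha). One-sided 10%: 80.3%. One-sided 5%: 68.7%.
- Risk difference 0.13: one-sided 10%, 89.2%; one-sided 5%, 81.0%.

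**Variants at one-sided 10%.** Reducing the sample to 254 for 10% loss gives hazard ratios of 1.70-1.73 / 1.90-1.95. Counting deaths as they would fall at the margin gives 1.58-1.59 / 1.72-1.74. Neither reaches 1.83 / 2.05. A Farrington-Manning calculation of the risk difference gives 0.1096 / 0.1324, the same as above.

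**How much of the gap is alpha.** In the 80% column the printed margins are 0.75 − 0.59 = 0.16 and 0.11.

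- Both at one-sided 10%: HR 1.66-1.68 gives survival 0.62, a margin of 0.13, against 0.11.
- Both at one-sided 5%: HR 1.81-1.84 gives survival 0.59, a margin of 0.16, against 0.13.

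Aligning alpha therefore moves the hazard-ratio row by about 3 points (141 × 0.03 ≈ 4 deaths per arm) or the risk-difference row by about 2 (141 × 0.02 ≈ 3). The other 2-3 points come from the change of scale.

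**The case against.** The strongest reply is that the text already names its margin, HR 1.83, and that the risk difference appears only in the table. If the 10% is two-sided, the named margin and its 80% power are about right, and the only error is in a supplementary row. This is correct as far as it goes, and it rules out several stronger readings that a reader might infer:

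- *That the decision threshold depends on which row is read.* The text points to the hazard ratio. The table's title does call both sets of figures margins, so confirming the scale is worthwhile, but the protocol is not silent on it.
- *That the 80% power for HR 1.83 is wrong.* This follows only if the 10% is one-sided, which the protocol does not say. Neither row on its own is shown to be wrong.
- *That the error is worth the whole gap of 16 against 11 points.* About half of that gap would remain after recomputing at one alpha. A result could still pass on one scale and fail on the other.
- *That the hazard ratios are exactly one-sided 5% values.* At 70.5 deaths neither formula gives 1.83 / 2.05 to two decimals. Freedman with 72 deaths (36 per arm) gives 1.829 / 2.053, but the protocol does not state that rounding. They are consistent with one-sided 5%, and no more can be claimed.

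It can also be said that mortality is a secondary outcome and that a full analysis plan is to follow. That plan may settle the sidedness, but it cannot make both printed rows true under one alpha.

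**Conclusion.** The inconsistency stands. Two error rates sit under one label, so at least one row of Table 1 has a stated power that is wrong: by about 8-10 points for HR 1.83 if alpha is one-sided 10%, or by about 11 points for a risk difference of 0.11 if alpha is two-sided 10%.

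This rests on the protocol's own inputs, on 1:1 allocation, and on standard large-sample formulas for log-rank and risk-difference comparisons. It does not touch the recruitment target: section 12.2 derives 282 from the sit-to-stand outcome, and Table 1 takes 282 as given. The primary estimand and its test are also unaffected.

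**What to change.** In section 12.1, state whether the 10% alpha is one- or two-sided. Confirm the hazard ratio as the decision scale, or name the risk difference instead. Then recompute every row of Table 1 at that alpha and name the formula and the number of deaths used. At 80% / 90% power:

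- One-sided 10%: HR about 1.66-1.68 / 1.84-1.88 (survival about 0.62 / 0.58-0.59); risk difference 0.11 / 0.13.
- One-sided 5% (two-sided 10%): HR about 1.81-1.84 / 2.01-2.07; risk difference 0.13 / 0.15.

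If the alpha is one-sided 10% and HR 1.83 is kept as the margin, its power should be given as about 88-90%. A sentence saying that the two scales are not expected to give equal margins would prevent misreading. The cost is one table and one paragraph, and it should be settled before mortality is compared by arm.

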12.2 Sample size calculation

The 30STS at 30 days post-randomisation is the primary outcome, a recommended outcome from our co-designed Core Outcome Set.⁴⁸ An international collaborative analysis of 451 critically ill patients from 5 studies, the STS mean (SD) at hospital discharge was estimated as 5.98(4.06).⁶³ A two repetition increase represents a minimal clinically important difference.⁸⁰ To detect this difference with 90% power at 5% significance level and assuming a common SD of 4.06 requires a total of 176 patients. Data from the Intensive Care national audit and research centre shows hospital mortality over the last three years to be 19.1%, 23.1% and 24.2%, and we have used 25% as a worst case scenario.⁶ In our previous eight-centre nutritional intervention trial we saw withdrawal related to clinical decisions, loss to follow-up and arm cross over, in 11 out of 121 patients (9%).⁸¹ Rounding these proportions up to be cautious, we have inflated the sample size to allow for 25% mortality, 10% loss to follow-up and 2% unplanned cross over. This yields a total number of **282** participants to recruit.

12.3 Metabolic data

In our pilot trial, untargeted metabolomic profiling was used in an exploratory fashion, to generate potential panels for future targeted work, coupled with targeted ketone and medium chain fatty acid analyses. The advantage of this approach was seen in the identification of panels separate from those that we would have used a priori e.g., energetic intermediate pathways such as TCA Cycle metabolites and NAD Metabolites. We are therefore in a position to apply both untargeted (to confirm our preliminary findings) and targeted metabolomics.

12.3.1 Ketone Flux, TCA cycle and Fatty Acid analysis

We will assess both routes of synthesis and metabolism of ketones through analyses of ketone precursors; plasma free fatty acids (C2-C24), ketone bodies and metabolites; Acetyl CoA, Acetoacetyl CoA, HMG-CoA, Malonyl-CoA, Mevalonate, as well as linked energetic intermediate pathways such as TCA Cycle metabolites and NAD Metabolites.

12.3.2 Amino acid and urea cycle flux

We will assess amino acid homeostasis through analysis of branch chain amino acids, glucogenic amino acids, ammonia, glutamine and their metabolites. Urea cycle flux will be assessed through analysis of 4-hydroxy-proline, ornithine, urea, and N-acetylornithine, citrulline, Aspartate, arginosuccinate, fumarate, arginine and their metabolites.

These targeted metabolite panels will be assessed using stable isotope labelled internal standard based concentration measurements using UHPLC-MS for each panel of metabolites, and metabolic modelling techniques such as stoichiometric metabolic flux analysis.⁸²

Data matrices of relative metabolite abundances will be log transformed, centered and scaled and exploratory visualisations generated using PCA/ PLSDA. To determine differences in metabolite abundance (both targeted panels and untargeted) as a result of the intervention, across time and interactions between intervention and time – analyses will be performed using a moderated empirical Bayesian mixed effects model approach with the limma R package.⁸³ For each comparison, False Discovery Rate correction will be applied using the Benjamini-Hochberg approach. Data sets will be reduced to only those metabolites important in differentiating temporality and intervention, relationships between changing metabolites and clinical variables determined using a combination of sparse redundancy analyses and canonical correlative analyses.^{84,85}

13. Ethics

The CI must ensure that the study is conducted in accordance with the guidelines of the International Conference on Harmonisation, Good Clinical Practice (GCP) and UK legislation. All study documentation will be reviewed and approved by the research ethics committee prior to start of recruitment. Research Ethics Committee, Health Research Authority and Sponsor approvals will be in place before patient recruitment commences. The study will be sponsored by Barts Health NHS Trust. Additionally, each participating site will ensure that the approval of the relevant trust Research & Development department and Ethics Committee is in place and a written confirmation is provided to the Sponsor.

14. Patient and Public Involvement

Patients and the Public have been actively involved in identifying the research topic, prioritising the research questions and in application preparation. Patient members have been drawn from nationwide critical care survivors support charities and local East London support groups. Both patient co-applicants and ICUsteps ([Home - ICUsteps](#)) reviewed the lay summary. Patients and relatives participated in the co-design of the Core Outcome Set. Patient focus groups have further informed and refined our application (focus on monitoring of diarrhoea) and reviewed our response to first stage comments (continuation of the intervention for 10 days regardless of ICU discharge). Patient members will help prepare the ethics submission and review patient information sheets and consent forms. A representative will attend trial steering group meetings, and review data on adverse events and outcomes. Panel members will interpret, analyse and frame safety and adverse events data especially in regard to the relevance and tolerability of diarrhoea. Panel members will be central to dissemination of findings both with the lay media and in professional education to ensure that these data reach the widest audience possible.

15. Data handling and record keeping

15.1 Data Management

Pseudonymised trial data will be transcribed onto the electronic CRF (eCRF) on the secure data entry web portal. All data will be pseudonymised at site, and a trial ID generated by the database. Age, patient initials and the trial ID will be used to identify the participants. The CRF will be designed by the database manager in the Critical Care and Perioperative Medicine Research group with input from the CI in accordance to Sponsor requirements. Only trial data related to the outcomes and data including safety events that will be used for statistical analysis will be collected. For participants that are withdrawn, data collected up to the point of withdrawal will be retained. Handling of withdrawal in terms of statistical analysis will be fully detailed in the statistical analysis plan.

Submitted data will be reviewed for completeness and consistency by authorised users within the trial coordinating team. Direct access to eCRF will be restricted, with only delegated and authorised users will be issued with (trial role related and defined) access to the eCRF. Each user will be assigned specific user roles and rights, and this will be reflected on the respective delegation log. Final sign-off by the site PI will be undertaken. Following data cleaning, a single final data lock will prevent changes to protect the final data set and will be exported from the study database for analysis by the trial statistician.

Storage and handling of confidential trial data and documents will be in accordance with the Data Protection Act 2018 (UK). A trial specific Data Management Plan will be developed by the coordinating team detailing all key methods of data management for collecting, recording, handling and storing of trial data. Transfer of patient identifiable information [contact] accounts and those used in [contact] will be secure and meet appropriate IT encryption and data protection requirements.

15.2 Source data

Source data is defined as all information in original patient records and certified copies of original records of clinical findings, observations, or other activities in a clinical trial necessary for the reconstruction and evaluation of the clinical investigation. Only members of the direct care team are entitled to have access to patients' medical records before consenting to the trial. Direct access will be granted to authorised representatives from the sponsor, host institution, and the regulatory authorities to permit study-related monitoring, audits, and inspections. Source data verification will be conducted in the eCRF.

15.3 Confidentiality

The PI has a responsibility to ensure that participant anonymity is protected and maintained. They must also ensure that their identities are protected from any unauthorised parties. The Sponsor will ensure that all participating partner organisations will maintain the confidentiality of all subject data and will not reproduce or disclose any information by which subjects could be identified, other than reporting of serious adverse events. In the case of special problems and/or competent authority queries, it is also necessary to have access to the complete trial records, provided that patient confidentiality is protected. Information with regards to study participants will remain confidential and managed in accordance with the Data Protection Act, NHS Caldicott Guardian, The UK Policy Framework for Health and Social Care Research Ethics Committee Approval. The CI and the study team will adhere to these parameters to ensure that the participant's identity is protected at every stage of their participation within the study. Patients will be anonymised with regards to any publications relating to this study.

15.4 Record retention and archiving

During the course of research, the CI has full responsibility of all study records which must be kept in secure conditions at all times. The UK Policy Framework for Health and Social Care Research and Sponsor SOP, requires that research records are kept for 25 years after

the study has completed. Archiving will be authorised by the Sponsor following submission of the end of study report. The Sponsor is responsible for maintaining and archiving the study TMF. The study database will be stored according to the Sponsor's policies. Electronic data sets will be stored indefinitely. The sites are responsible for maintaining and archiving all local records including the ISF and CRFs. These records should be archived together once authorisation has been given by the Sponsor. It is the responsibility of the PI to ensure a full set of records is collated and documented.

16. Laboratories

Samples will be stored centrally at the William Harvey Institute at Queen Mary University of London, until sent out as batches to laboratories for analyses.

16.1 Central laboratories

Study specific sample analysis will be performed as follows:

- 1) Beta-hydroxybutyrate and lactate analysis will be performed at Laboratory of Clinical Chemistry, University College London, Institute of Child Health.
- 2) Metabolomic analysis will be performed at Centre of Metabolism, Ageing and Physiology, University of Nottingham Medical School at Derby
- 3) Whole blood leucocyte gene expression analysis will be performed at Wellcome Trust Centre for Human Genetics, Henry Wellcome Building of Genomic Medicine.
- 4) Leucocyte gene expression analysis will be performed at [name] laboratory, University of Exeter Medical School.

16.2 Sample collection, labelling and logging

The following blood samples will be collected for all participants:

- 2x 6ml EDTA tubes will be collected for plasma separation for metabolomics and ketone body analysis at day one and day seven from point of randomisation.
- 1x 2.5ml whole blood will be collected for extra study specific bloods for leucocyte gene expression analysis at day 1 and day 7.
- 2x 10ml Whole blood will be collected for future study of immunological and metabolic assessments on days 1 and 7.

All blood samples will be pseudo-anonymised. Samples collected at each participating site will be labelled with the participant's corresponding trial ID and kept in a hospital freezer. The samples will be routinely collected and transferred to William Harvey Research Institute prior

to transfer to the different central laboratories by an approved courier company. The full sample, collection, labelling, logging and transfer procedure will be documented in the study laboratory log. The trial coordinating team will provide sites with a SOP on sample collection, processing and storage.

16.3 Sample receipt/ chain of custody/ accountability

Handling of the samples upon arrival at the local and central laboratory will be documented. All samples will be logged upon receipt and the laboratory will ensure that the physical integrity of these samples have not been compromised in transit. If compromise has occurred, the trial coordinating team, as well as the Sponsor, will be informed of this. Upon receipt of samples, laboratory staff will ensure that all samples are accounted for as per the labelling.

16.4 Sample storage procedures

The samples will be stored in pseudo-anonymised form with the participant's trial ID written on the label in a local hospital freezer at an optimal temperature for the troponin assay until collection. The samples should be put in the freezer within two hours of preparation. The samples will not be destroyed if a patient withdraws from the study unless they specifically request so. If the patient requests for the samples to be destroyed the Tissue Custodian (CI), will inform the lab who will ensure the samples are destructed as per the Human Tissue Act. This will be documented in the TMF and ISF of the participating site.

